11.8 Concomitant medication

Table 11.8.1 Concomitant medication ATC1*ATC2

ATC codes	Dose Cohort			
	1.5 mg N=X	2.0 mg N=X	2.5 mg N=X	Total N=X
	n (%)			
ATC1				
ATC2				
ATC2				
ATC1				
ATC2				

Table 11.8.2 Concomitant medication ATC1*ATC2*ATC4*PN

ATC1 ATC2	Dose Cohort			
	1.5 mg N=X	2.0 mg N=X	2.5 mg N=X	Total N=X
	n (%)			
ATC1				
ATC2				
ATC4				
PN				
ATC1				
ATC2				
ATC4				
PN				

Table 11.8.3 Requirement of another specific treatment for COVID-19

Specific treatment for COVID-19	1.5 mg N=X		2.0 mg N=X		2.5 mg N=X		Total N=X	
	N	%	N	%	N	%	N	%
Yes								
No								

Table 11.8.4 Support treatment requirements

Support treatment requirements	1.5 mg N=X		2.0 mg N=X		2.5 mg N=X		Total N=X	
	N	%	N	%	N	%	N	%
Yes								
No								

Table 11.8.5 Support treatment ATC1*ATC2*ATC4

Support treatment	Dose Cohort			
	1.5 mg N=X	2.0 mg N=X	2.5 mg N=X	Total N=X
	n (%)			
ATC1*ATC2*ATC4				

Table 11.8.6 Concomitant treatment duration

Days	Dose Cohort																	
	1.5						...						Total					
	N	Mean	Median	Range	Q1	...*	N	Mean	Median	Range	Q1	...*
Corticosteroids treatment																		
Antibiotic treatment																		

(*) Q3 and Std.

APPENDIX III

12 EFFICACY EVALUATION

12.1 Efficacy evaluation

Table 12.1.1 Number of patients with PCR

Number of patients with PCR	Dose Cohort			
	1.5 mg N=X	2.0 mg N=X	2.5 mg N=X	Total N=X
Baseline				
Undetectable				
Positive				
Day ...				

Table 12.1.2 Viral load classification by dose level and total

Day	Viral Load at baseline (copies/mL)	Viral Load classification during treatment (copies/mL)			
		Low <4	Medium [4-7]	High >7	Total
Day 4	Low <4				
	Medium [4-7]				
	High >7				
	Total				
...(*)	Low <4				
	Medium [4-7]				
	High >7				
	Total				

(*) Days 7, 15 and 31

Listing 12.1.3 Viral load evolution

Subject id	Dose	Visit	Result	log10 viral load copies/mL

Table 12.1.4 Summary of Protocol-Specified Efficacy Endpoints. Cumulative results.

Endpoint from day 1 to	Dose Cohort			
	1.5 mg N=X	2.0 mg N=X	2.5 mg N=X	Total N=X
Patients discharged from hospital, n (%)				
Day 7				
Day 8				
Day 15				
Day 31				
Deaths at, n (%)				
Day 7				
Day 15				
Day 31				
Later than Day 31				
Patients requiring invasive mechanical ventilation and/or ICU admission at, n (%)				
Day 7				
Day 15				
Day 31				
Patients requiring invasive mechanical ventilation, n (%)				
Day 7				
Day 15				
Day 31				
Patients requiring ICU admission at, n (%)				
Day 7				
Day 15				
Day 31				
Patients requiring non-invasive mechanical ventilation at, n (%)				
Day 7				
Day 15				
Day 31				
Patients requiring oxygen therapy at, n (%)				
Day 7				
Day 15				
Day 31				
Patients requiring oxygen therapy (high flow) at, n (%)				
Day 7				
Day 15				
Day 31				
Patients requiring oxygen therapy (low flow) at, n (%)				
Day 7				
Day 15				
Day 31				

This table will be also performed by age (<65 vs. ≥65 year old (12.1.4.1)

This table will be also performed by FDA classification (12.1.4.2)

Table 12.1.5 Summary of Protocol-Specified Efficacy Endpoints. Non-cumulative results.

Endpoint	Dose Cohort			
	1.5 mg N=X	2.0 mg N=X	2.5 mg N=X	Total N=X
Patients discharged from hospital, n (%)				
Day 1 to Day 8				
Day 9 to Day 15				
Day 16 to Day 31				
Deaths at, n (%)				
Day 1 to Day 7				
Day 8 to Day 15				
Day 16 to Day 31				
Later than Day 31				
Patients requiring invasive mechanical ventilation and/or ICU admission at, n (%)				
Day 1 to Day 7				
Day 8 to Day 15				
Day 16 to Day 31				
Patients requiring invasive mechanical ventilation, n (%)				
Day 1 to Day 7				
Day 8 to Day 15				
Day 16 to Day 31				
Patients requiring ICU admission at, n (%)				
Day 1 to Day 7				
Day 8 to Day 15				
Day 16 to Day 31				
Patients requiring non-invasive mechanical ventilation at, n (%)				
Day 1 to Day 7				
Day 8 to Day 15				
Day 16 to Day 31				
Patients requiring oxygen therapy at, n (%)				
Day 1 to Day 7				
Day 15				
Day 31				
Patients requiring oxygen therapy (high flow) at, n (%)				
Day 7				
Day 15				
Day 31				
Patients requiring oxygen therapy (low flow) at, n (%)				
Day 7				
Day 15				
Day 31				

This table will be also performed by age (<65 vs. ≥65 year old) (12.1.5.1)

This table will be also performed by FDA classification (12.1.5.2)

Table 12.1.6 Summary of Protocol-Specified Efficacy Endpoints 95%CI

Dose Cohort															
1.5 mg				2 mg				2.5 mg				Total			
N	%	Exact CI Lower	Exact CI Upper	N	%	Exact CI Lower	Exact CI Upper	N	%	Exact CI Lower	Exact CI Upper	N	%	Exact CI Lower	Exact CI Upper

(*) Patients requiring Invasive Mechanical Ventilation; Patients requiring Non Invasive Mechanical Ventilation; Patients requiring ICU.

This table will be also performed by age (<65 vs. >=65 year old (12.1.6.1)
This table will be also performed by FDA classification (12.1.6.2)

Table 12.1.7 Viral load change from baseline and negative detection

Mean change in viral load from baseline to, log10 copies/mL	Dose Cohort			
	1.5 mg N=X	2.0 mg N=X	2.5 mg N=X	Total N=X
Day 4				
Day 7				
Day 15				
Day 31				
Mean time from baseline until undetectable viral load (days)*				

All patients (12.1.7.1), Mild & moderate patients (12.1.7.2), moderate patients (12.1.7.3), severe patients (12.1.7.4).

(*) From baseline PCR

Table 12.1.8 Viral load at baseline and study outcome variables

	Viral Load at baseline			
	Low <4	Medium [4-7]	High >7	p-value(*)
Oxygen therapy				
Yes				
No				
Oxygen therapy Low flow				
Yes				
No				
Oxygen therapy High flow				
Yes				
No				
ICU admission				
Yes				
No				
NIMV				
Yes				
No				
IMV				
Yes				
No				
Death				
Yes				
No				
Days of hospitalization				
FDA Risk groups				
Mild				
Moderate				
Severe				

(*)Fisher's exact test for categorical variables. Kruskal-Wallis test for continuous variables.

Table 12.1.9 Patients with negative detection

Number of patients (%)	Dose Cohort			
	1.5 mg N=X	2.0 mg N=X	2.5 mg N=X	Total N=X
Day 4				
Day 7				
Day 15				
Day 31				

Table 12.1.10 Patients with negative detection according to initial viral load

Number of patients (%)	Dose Cohort			
	1.5 mg N=X	2.0 mg N=X	2.5 mg N=X	Total N=X
Low <4				
Medium [4-7]				
High >7				
Total				

Table 12.1.11 Time to negative detection

Time to negative detection	Time to negative detection			p-value(**)
	N	Median	Range	
Viral load at baseline				
Low <4				
Medium [4-7]				
High >7				
Dose				
1.5 mg				
2.0 mg				
2.5 mg				
Age				
< 65 y.o.				
>=65 y.o.				
Sex				
Female				
Male				
Race				
White				
Other				
... (*)				

(*) FDA risk groups (Mild, moderate, severe), Oxygen need (Yes/No), Chronic lung disease (Yes/No), Corticosteroids (Yes/No), Other antiviral treatment for COVID-19 (Yes/No). Further variables could be added upon request

(**) Kruskal-Wallis

Table 12.1.12 Time to negative detection by corticosteroid duration

Time to negative detection	Corticosteroid duration		p-value*
	< 10 days	>= 10 days	
Dose			
1.5 mg			
2.0 mg			
2.5 mg			
Total			

(**) Kruskal-Wallis

Table 12.1.13 Oxygen therapy

Number of patients (%)	Dose Cohort							
	1.5 mg N=X		2.0 mg N=X		2.5 mg N=X		Total N=X	
	Oxygen therapy							
	Yes	No	Yes	No	Yes	No	Yes	No
Oxygen therapy at baseline								
Yes								
No								
Chronic Lung Disease								
Yes								
No								
Age								
< 65 y.o.								
>=65 y.o								
Gender								
Female								
Male								
Race								
White								
Other								
Viral load at baseline								
Low <4								
Medium [4-7]								
High >7								
FDA Risk groups								
Mild								
Moderate								
Severe								

Listing 12.1.14 Oxygen therapy evolution

Subject id	Dose	Visit	Date	Time	Oxygen therapy type	Flow

Table 12.1.15 Oxygen therapy onset day

Onset day	Dose Cohort							
	1.5 mg N=X		2.0 mg N=X		2.5 mg N=X		Total N=X	
From start of symptoms								
From first plitidepsin dose								
From corticosteroids use								

Table 12.1.16 Patients changing oxygen therapy

	Dose Cohort			
	1.5 mg N=X	2.0 mg N=X	2.5 mg N=X	Total N=X
From no Oxygen therapy to Oxygen therapy				
From low flow to high flow				
From high flow to low flow				

Table 12.1.17 Time in (ICU- Invasive M Ventilation – Non Invasive MV – in Hospital)

Time (days)	Dose Cohort			
	1.5 mg N=X	2.0 mg N=X	2.5 mg N=X	Total N=X
ICU				
Invasive mechanical ventilation				
Non Invasive mechanical ventilation				
Hospital*				

(*)From first infusion

Table 12.1.18 Reason for ICU discharge

Endpoint	Dose Cohort			
	1.5 mg N=X	2.0 mg N=X	2.5 mg N=X	Total N=X
Reason for ICU discharge, n (%)				
Taken back to the ward				
Death				

Table 12.1.19 ICU admission according to oxygen therapy or chronic lung disease

Number of patients (%)	Dose Cohort							
	1.5 mg N=X		2.0 mg N=X		2.5 mg N=X		Total N=X	
	ICU admission*							
	Yes	No	Yes	No	Yes	No	Yes	No
Oxygen therapy at baseline								
Yes								
No								
Chronic Lung Disease								
Yes								
No								

(*) on day 7, 15 and 31.

Table 12.1.20 ICU admission

	Dose Cohort			
	1.5 mg N=X	2.0 mg N=X	2.5 mg N=X	Total N=X
Antiviral, n (%)				
Yes				
No				
Use of corticosteroids, n (%)				
Yes				
No				
Other COVID-19 treatment, n (%)				
Yes				
No				
High flow oxygen				
Yes				
No				
Invasive mechanical ventilation, n (%)				
Yes				
No				
Non-invasive mechanical ventilation, n (%)				
Yes				
No				

Table 12.1.21 ICU admission onset day and time to hospital discharge

Onset Day	Dose Cohort							
	1.5 mg N=X		2.0 mg N=X		2.5 mg N=X		Total N=X	
From first plitidepsin dose								
From onset of symptoms								
From ICU admission to hospital discharge								

Table 12.1.22 Hospital discharge

Endpoint	Dose Cohort							
	1.5 mg N=X		2.0 mg N=X		2.5 mg N=X		Total N=X	
Hospital discharge, n (%)								
Yes								
No								
Reason								

Table 12.1.23 Time to Hospital discharge

Days	Dose Cohort							
	1.5 mg Median (range)		2.0 mg Median (range)		2.5 mg Median (range)		Total Median (range)	
From first dose								
From admission								

Table 12.1.24 Multivariate analysis Hospital discharge on day 8

Variable	Value	DF	Estimate	Standard error	Wald Chi-Square	Pr > Chi-Square	Effect	Odds Ratio Estimate	Lower 95% Confidence Limit for Odds Ratio	Upper 95% Confidence Limit for Odds Ratio
..										

(*) Logistic regression.

Table 12.1.25 Multivariate analysis Hospital discharge on day 15

Variable	Value	DF	Estimate	Standard error	Wald Chi-Square	Pr > Chi-Square	Effect	Odds Ratio Estimate	Lower 95% Confidence Limit for Odds Ratio	Upper 95% Confidence Limit for Odds Ratio
..										

(*) Logistic regression.

Table 12.1.26 Multivariate analysis Time to hospital discharged

Parameter	DF	Parameter Estimate	Standard error	Chi-Square	Hazard Ratio	95% Lower Confidence Limit for Hazard Ratio	95% Upper Confidence Limit for Hazard Ratio	Pr > ChiSq
...								

(*) Cox regression.

Table 12.1.27 Invasive mechanical ventilation

Number of patients (%)	Dose Cohort							
	1.5 mg N=X		2.0 mg N=X		2.5 mg N=X		Total N=X	
	Invasive mechanical ventilation*							
	Yes	No	Yes	No	Yes	No	Yes	No
Oxygen therapy at baseline								
Yes								
No								
Chronic Lung Disease								
Yes								
No								

(*) at day 4, 7, 15 and 31.

Table 12.1.28 Invasive mechanical ventilation with prior/further non-invasive mechanical ventilation or oxygen therapy

	Dose Cohort			
	1.5 mg N=X	2.0 mg N=X	2.5 mg N=X	Total N=X
Prior Non-invasive mechanical ventilation, n (%)				
Yes				
No				
Further Non-invasive mechanical ventilation, n (%)				
Yes				
No				
Prior oxygen therapy, n (%)				
Yes				
No				
Further oxygen therapy, n (%)				
Yes				
No				
Further oxygen therapy Low flow, n (%)				
Yes				
No				
Further oxygen therapy High Flow, n (%)				
Yes				
No				
Other COVID-19 treatment, n (%)				
Yes				
No				

Table 12.1.29 Invasive mechanical ventilation onset day

Onset day	Dose Cohort							
	1.5 mg N=X		2.0 mg N=X		2.5 mg N=X		Total N=X	
From start of symptoms								
From first plitidepsin dose								
From corticosteroids use								

Table 12.1.30 Non-invasive mechanical ventilation with prior invasive mechanical ventilation or oxygen therapy

	Dose Cohort			
	1.5 mg N=X	2.0 mg N=X	2.5 mg N=X	Total N=X
Prior invasive mechanical ventilation, n (%)				
Yes				
No				
Oxygen therapy, n (%)				

Yes				
No				
Other COVID-19 treatment, n (%)				
Yes				
No				

Table 12.1.31 Non-invasive mechanical ventilation onset day

Onset day	Dose Cohort			
	1.5 mg N=X	2.0 mg N=X	2.5 mg N=X	Total N=X
From start of symptoms				
From first plitidepsin dose				
From corticosteroids use				

Table 12.1.32 Six-point ordinal scale

Treatment day	n (%)	Dose Cohort			
		1.5 mg N=X	2.0 mg N=X	2.5 mg N=X	Total N=X
Day 7	1 Discharge (Alive)				
	2 Hospital admission, not requiring supplemental oxygen				
	...				
Day ...*	1 Discharge (Alive)				
	2 Hospital admission, not requiring supplemental oxygen				
	...				

(*) On days 15 and 31

Table 12.1.33 Six-point ordinal scale shift table

Treatment day	Baseline 6-point ordinal scale	6-point ordinal scale			
		1 Discharge (Alive)	2 Hospital admission, not requiring supplemental oxygen	...	Total
Day 7	1 Discharge (Alive)				
	2 Hospital admission, not requiring supplemental oxygen				
	...				
Day ...*	1 Discharge (Alive)				
	2 Hospital admission, not requiring supplemental oxygen				
	...				

(*) On days 15 and 31. It could be done by dose, if requested.

Table 12.1.34 Two points improvement in Six-point ordinal scale or discharged by day

[figure not shown]
Two points improvement or discharged	Dose Cohort			
	1.5 mg N=X	2.0 mg N=X	2.5 mg N=X	Total N=X
Day 7				
Day 15				
Day 31				

Table 12.1.35 FDA risk groups

	FDA risk groups at baseline			
	Mild	Moderate	Severe	p-value
Non-invasive mechanical ventilation, n (%)				
Yes				
No				
Invasive mechanical ventilation, n (%)				
Yes				
No				
High flow oxygen therapy, n (%)				
Yes				
No				
ICU admission, n (%)				
Yes				
No				
Days of hospital admission				
Days of symptom evolution				
CRP				
Ferritin				
AST				
ALT				
LDH				
Lymphocytes				

[figure not shown]
(*)It could be done by dose, if requested.

Figure 12.1.36 Plitidepsin: Viral load by Dose level (Median)

The lines represent the median value from baseline of the patients treated with viral load by central lab at the three dose levels in each time point(1.5mg n=x, 2.0 mg n=x, 2.5 mg n=x)

Figure 12.1.37 Plitidepsin: Viral load by Dose level (Mean)

The lines represent the mean value from baseline of the patients treated with viral load by central lab at the three dose levels in each time point (1.5mg n=x, 2.0 mg n=x, 2.5 mg n=x)

Figure 12.1.38 Plitidepsin: Viral load by FDA classification at baseline (Median)

[figure not shown]

Figure 12.1.39 Plitidepsin: Viral load by FDA classification at baseline (Mean)

[figure not shown]

Figure 12.1.40 Plitidepsin: Viral load by Oxygen support on day 1 (Median)

[figure not shown]

Figure 12.1.41 Plitidepsin: Viral load by Oxygen support on day 1 (Mean)

[figure not shown]
[figure not shown]
[figure not shown]

Figure 12.1.42 Time to negative detection of COVID-19 detection by PCR

[figure not shown]
(*) Table 12.1.37 will be also produced with median value and 95% confidence interval.

Figure 12.1.43 Time to Hospital discharge

[figure not shown]
(*) Table 12.1.38 will be also produced with median value and 95% confidence interval.

Figure 12.1.44 Time to Hospital discharge – All patients

[figure not shown]
(*) Table 12.1.39 will be also produced with median value and 95% confidence interval.

Figure 12.1.45 Time to Hospital discharge by FDA classification

(*) Table 12.1.40 will be also produced with median value and 95% confidence interval.

Figure 12.1.46 Time to Hospital discharge by time from symptoms (≤ 6 days vs >6 days)

(*) Table 12.1.41 will be also produced with median value and 95% confidence interval.

Figure 12.1.47 Swimmer Plot of Hospital Discharge Day by Viral Load at Baseline

[figure not shown]

Figure 12.1.48 Swimmer Plot of Hospital Discharge Day by Disease Severity at Baseline

[figure not shown]

Figure 12.1.49 Swimmer Plot of Oxygen therapy

[figure not shown]

Figure 12.1.50 Viral load evolution per patient

[figure not shown]

Figure 12.1.51 Viral load and C-reactive protein evolution per patient

[figure not shown]

Figure 12.1.52 Viral load and C-reactive protein evolution by dose

[figure not shown]

Figure 12.1.53 Viral load and C-reactive protein evolution by baseline level

[figure not shown]

Figure 12.1.54 Viral load and LDH evolution per patient

[figure not shown]

Figure 12.1.55 Viral load and LDH evolution by dose

[figure not shown]

Figure 12.1.56 Viral load and LDH evolution by baseline level

[figure not shown]

Figure 12.1.57 Viral load and Ferritin evolution per patient

[figure not shown]

Figure 12.1.58 Viral load and Ferritin evolution by dose

[figure not shown]

Figure 12.1.59 Viral load and Ferritin evolution by baseline level

[figure not shown]

Figure 12.1.60 D-dimer median graph

[figure not shown]

Figure 12.1.61 D-dimer evolution by dose

[figure not shown]

Figure 12.1.62 Viral load and D-dimer evolution by baseline level

[figure not shown]

Figure 12.1.63 Viral load and Lymphocytes evolution per patient

[figure not shown]

Figure 12.1.64 Viral load and Lymphocytes evolution by dose

[figure not shown]
[figure not shown]

Figure 12.1.65 Viral load and Lymphocytes evolution by baseline level

Listing 13.5 Laboratory parameters. Biochemical (III)

Arm	Center	Subject id.	Visit	Date	ALP IU/L	ALP change %	BIL mg/dL	BIL change %	CPK IU/L	CPK change %	Creatinine mg/dL	Creatinine change %	CRP mg/L	CRP change%

Glucose, ALT, AST, GGT, LDH, Troponin, Ferritin

Listing 13.6 Other COVID-19 treatment (I)

Arm	Center	Subject id.	Other covid treatment	Clorine/ hydroxychloroquine	Tocilizumab	Remdesivir	Lopinavirritonavir	IFN B 1B

Other, other specify:

Listing 13.6 Other COVID-19 treatment . Support treatment (II)

Arm	Center	Subject id.	Antibiotic	Azitromizina	Other Antibiotic	Other Antibiotic:	Antifungal Agents	Other support treatment

Listing 13.6 Other COVID-19 treatment Corticosteroids (III)

Arm	Center	Subject id.	Corticosteroids	Corticosteroids Onset day	Corticosteroids Duration (days)	Corticosteroid total daily dose

Listing 13.7 Concomitant medication or procedures

Arm	Center	Subject id.	Medication / Procedure	Description	Use	Active substance	Code (ATC)	Start date	Ongoing	End date	Dose	Units

Frequency, Route, Indication, Specify.

Listing 13.8 End of study

Arm	Center	Subject id.	End of Study	Reason	End of study date	Follow-up time

Listing 13.9 Deaths

Arm	Center	Subject id.	End of treatment	Cause of death	Specify	Adverse event	Grade	Relationship

Listing 13.10 Protocol deviations

Arm	Center	Subject id.	Deviation date	Category	Deviation type	Reason (text)

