Intra-patient dose change/increase is not allowed.

Once the 27 patients (9 at each dose level) contemplated in the study protocol have been included, an extension period will be opened to include 18 additional patients (6 at each plitidepsin dose level) to extend the collection of safety information on the different doses and additionally to collect efficacy data. After this extension period, data will be available for 15 patients at each plitidepsin dose level.

During the extension period, patients will be randomised in a 1:1:1 ratio as appropriate to each dose level (arm).

During the extension period of the study, if in any of the arms, 2 or more patients present an adverse event classed as grade 3 or higher related to plitidepsin, the sponsor will interrupt the recruitment of new patients at that dose level and higher, and will assess jointly with the Spanish Agency of Medicines and Medical Devices the convenience of continuing recruitment in that arm and in arms with a higher dose. Additionally, the sponsor will forward weekly follow

up records to the Spanish Agency of Medicines and Medical Devices, with the information of all the adverse event classed as grade 3 or higher, reported, whether or not related to plitidepsin, for review and joint assessment if necessary.

After the joint evaluation of the safety and efficacy data obtained in the present study between the sponsor and the Spanish Agency of Medicines and Medical Devices, the recommended dose level will be selected to evaluate the efficacy of the treatment in patients with COVID-19 in a subsequent randomised phase II/III study.

The final statistical analysis that will be the basis of the final report of the study will be done on the total population of 45 patients once the extension of the study has been completed.. The data of the first 27 patients will be analysed in an intermediate statistical analysis.

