#### Secondary objectives:

- To assess the efficacy of plitidepsin in patients with COVID-19 at the proposed dose levels by:
  - o Change in SARS-CoV-2 viral load from baseline
  - o Time until negative detection of SARS-CoV-2 by PCR
  - o Cumulative incidence of disease severity. The evaluation will be based on:
    - Mortality
    - Need for invasive mechanical ventilation and/or ICU admission
    - Need for non-invasive mechanical ventilation
    - Need for oxygen therapy
- Selection of the recommended dose levels of plitidepsin for a phase II/III efficacy study

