## **12. STATISTICAL CONSIDERATIONS**

### **12.1. General considerations**

This section describes the main analyses that will be carried out. The statistical analysis plan to be approved by the sponsor will include additional information on analyses, management of unavailable data and analytical methods. All data will be analysed with the SAS statistical analysis system. All analyses will be carried out mainly by descriptive statistical methods. Continuous endpoints will be described using mean and standard deviation, median, minimum, maximum, Q1 and Q3. Categorical endpoints will be described with frequencies and percentages as well as the exact 95% confidence interval of the relevant study variables. All results will be presented separately by treatment arm.

The final statistical analysis that will be the basis of the final report of the study will be done on the total population of 45 patients once the extension of the study has been completed. The data of the first 27 patients will be analysed in an intermediate statistical analysis.

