3.1 Analyses to perform by cohort in the interim analysis

3.1.1 First analysis: First group (3 patients)

The first group of 3 patients will be from treatment arm A. After patients have completed 12 days from the last plitidepsin administration, a safety analysis will be performed.

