3.1.5 Fifth analysis: Fifth group (3 patients)

If the last analysis concludes that the study can be continued, 3 new patients will be recruited, who will be included in the arm C, if the previous analysis does not involve the closure of this arm. When these patients finish the 12 days follow-up period from the last plitidepsin administration, the new patients will be analysed and an aggregate analysis with all the study patients will be performed.

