8.1 Efficacy evaluation

The following tests will be performed to evaluate the efficacy of the treatment:

a) Viral load evolution:

For the analysis of the evolution of the viral load, the number and percentage of patients from who a sample has been collected will be indicated to determine the viral load at baseline and at visit 4, 7, 15 and 31 describing the results in those patients (number of RNA copies detected and log of the number of copies). The result will be given to three decimal places.

The graphs of the evolution of the viral load (mean and median) of the patients from the baseline to the last visit will be presented. These graphs will be shown by separate for each dose level, by FDA baseline classification and Oxygen support or not on day 1.

In addition, the following variables will be analyzed:

- The number and percentage of patients who viral load result is maintained, decreased or increased with respect to the previous visit on days 4, 7, 15 and 31 will be presented.
- Negative detection (global and by dose level):
- The number and percentage of patients with negative or undetectable viral load on days 4,7,15 and 31.
- The number and percentage of patients with negative or undetectable viral load on days 4,7,15 and 31 in the subgroups of low, medium and high initial viral load.
- Time to negative detection (viral load 0 or undetectable) in overall patients from date of PCR at baseline.
- Time to negative detection (viral load 0 or undetectable) based on baseline viral load (high (>7 copies/mL) / medium [4-7 copies/mL] / low (<4 copies/mL)) and other baseline characteristics (sex, age, race, ...) will be explored.
- Time to negative detection based on corticosteroid treatment (<10 days vs > 10 days)
- Viral load (high, medium, low) will be correlated with study outcome variables such as need for oxygen therapy, admission to ICU (Yes / No), NIMV, IMV, days of hospitalization, death (Yes / No).

- Determine the relationship between the number of days with symptoms and having a higher or lower viral load.
- Determine the relationship between viral load and the baseline situation of the patient, mild-moderate-severe, oxygen need / no need.
- The relationship between viral load and different inflammatory parameters (LDH, ferritin, C-reactive protein, D-dimer and lymphocytes) will be graphically analyzed.
- The mean change in viral load log₁₀ RNA copies/mL from baseline to day 4, 7, 31 will be analyzed in:
 - All patients

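### Viral load change by dose is planned as raw means with no confidence interval and no adjustment for baseline viral load or time since symptom onset

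*SAP*

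**What the plan says.** Change in viral load from baseline is the first secondary endpoint listed in the protocol (1.11 and 6.3) and the SAP (2.6). Its by-dose summary on the log10 scale is SAP Table 12.1.7, whose entry is "Mean change in viral load from baseline to, log10 copies/mL" at Days 4, 7, 15 and 31. The table is repeated by FDA severity group. SAP 8.1 a) also asks only for the mean change.

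The general rules go further than the shell. SAP section 3 and protocol 12.1 both ask for the SD, median and quartiles of continuous variables. Neither asks for a confidence interval for a mean. Intervals are planned for proportions (Table 12.1.6) and Kaplan-Meier medians.

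The SAP treats both covariates as relevant to viral load. It plans to "Determine the relationship between the number of days with symptoms and having a higher or lower viral load", and Table 10.2.1 shows baseline viral load and time from onset to first dose by dose cohort. Its regression models, however, concern hospital discharge (8.1 l) and Figure 15.4.1).

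On use and size, a secondary objective is "Selection of the recommended dose levels of plitidepsin for a phase II/III efficacy study". Protocol 1.9 says the dose will be selected after joint evaluation of safety and efficacy data. It also says "After this extension period, data will be available for 15 patients at each plitidepsin dose level", and the final analysis is to be "done on the total population of 45 patients once the extension of the study has been completed".

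On allocation, "The first group of 3 patients will be from treatment arm A" (SAP 3.1.1), and for the fifth group "3 new patients will be recruited, who will be included in the arm C" (SAP 3.1.5).

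**The concern.** Protocol 5.2 calls the trial uncontrolled, so the three doses side by side are its only internal efficacy comparison. A patient who starts with a higher viral load has more room to fall, and a patient treated later in the illness may already be clearing virus. Entry is allowed up to 10 days after onset, so time since onset can differ widely between patients. With 15 per arm, either factor can differ enough between arms to imitate or hide a dose effect.

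A bare mean also gives the sponsor and the agency no sense of how far apart two dose means must be before the gap is worth attention. The plan gives intervals for ventilation and ICU admission and a covariate-adjusted model for discharge. It gives neither for the endpoint closest to the drug's proposed antiviral action.

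**Working it through.** **The plan's own figures.** 9 + 6 = 15 per dose and 27 + 18 = 45 in total; both reproduce. The documents state no power, target difference or SD for viral load. The SDs (1.0 to 2.0 log10) and the baseline to follow-up correlations r (0.3 to 0.7) below are therefore assumptions. The SD is taken as equal at baseline and follow-up.

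**Chance imbalance at baseline.** The standard error of the difference in mean baseline between two arms is SD × √(2/15) = 0.365 × SD. For SD 1.0 / 1.5 / 2.0 this is 0.37 / 0.55 / 0.73 log10, with a 95% range (× 1.96) of ±0.72 / ±1.07 / ±1.43.

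**How much reaches the change score.** Subtracting baseline removes a share r of the imbalance and leaves (1 − r). At SD 1.5 and r = 0.3 / 0.5 / 0.7, an imbalance of one standard error shifts the difference in mean change by 0.38 / 0.27 / 0.16 log10. The 95% range of that shift is ±0.75 / ±0.54 / ±0.32.

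**Precision of a difference between two doses, 15 per arm.**

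- Raw change: half-width = t(28 df) × SD × √(2(1 − r)) × √(2/15)
- ANCOVA on baseline: half-width = t(27 df) × SD × √(1 − r²) × √(2/15)
- Variance ratio, ANCOVA to raw change: (1 − r²) / (2(1 − r)) = (1 + r)/2

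| SD (log10) | r | Raw change | ANCOVA | Variance ratio |
|---|---|---|---|---|
| 1.0 | 0.3 | 0.89 | 0.71 | 0.65 |
| 1.0 | 0.5 | 0.75 | 0.65 | 0.75 |
| 1.0 | 0.7 | 0.58 | 0.54 | 0.85 |
| 1.5 | 0.3 | 1.33 | 1.07 | 0.65 |
| 1.5 | 0.5 | 1.12 | 0.97 | 0.75 |
| 1.5 | 0.7 | 0.87 | 0.80 | 0.85 |
| 2.0 | 0.3 | 1.77 | 1.43 | 0.65 |
| 2.0 | 0.5 | 1.50 | 1.30 | 0.75 |
| 2.0 | 0.7 | 1.16 | 1.07 | 0.85 |

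The ANCOVA column covers baseline viral load only. The documents give nothing from which to size the effect of days since onset.

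**One arm's mean.** For an SD of change of 1.0 / 1.5 / 2.0 log10 and n = 15, the half-width is 0.55 / 0.83 / 1.11 log10.

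**Moderate patients (Table 12.1.7.3).** The at-risk table under SAP Figure 15.1.2 starts with 23 moderate patients. An even split (assumed) gives 23/3, about 8 per arm. The half-width for a dose difference is then 1.07 to 2.14 log10 for an SD of change of 1.0 to 2.0.

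**Imbalance that is not chance.** Taking the group sizes in the SAP 3.1 headings (3 + 6 + 9 + 6 + 3 = 27), arms A and C are randomised side by side only in the third group (3 each) and the extension (6 each). That is 9 against 9 of the planned 15 against 15. The remaining patients in A were enrolled before C opened, and the remaining patients in C after A had reached 9. The text of SAP 3.1.4 gives 9 patients where its heading gives 6, so this count depends on the heading being the intended reading.

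**The case against.** The strongest reply is that this is a descriptive safety study. Protocol 12.5.1 has efficacy analysed separately at each dose, and no contrast, test or ranking rule is defined for viral load change. The dose is chosen on safety and efficacy together, and nothing gives this mean a deciding role. This stands, and it is why a model should be supportive and exploratory. It does not remove the need for an interval: the doses are tabulated side by side, one must be selected, and Table 12.1.11 already plans a p-value by dose for time to negative detection.

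A second reply is that the plan handles part of the problem. The SD is required by general rule. Baseline viral load and time from onset are shown by dose. Negative detection is shown by dose within baseline viral load class (Table 12.1.10), and mean change is repeated by severity. All of this is correct. It makes an imbalance visible but does not adjust the mean change for it, and severity is neither baseline viral load nor symptom duration.

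A third is that the gain is modest and the model incomplete. This also stands. At r = 0.7 and SD 1.5 the half-width falls only from 0.87 to 0.80. The SAP expects results of zero or undetectable, for which log10 is undefined without a rule. Covariate adjustment also cannot remove differences due to calendar time.

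**Conclusion.** The point holds in a limited form. No confidence interval is planned for mean viral load change by dose, and no adjustment for baseline viral load or days since onset, although both are collected and efficacy data inform the dose. At SD 1.5 log10, r = 0.5 and 15 per arm, adjustment for baseline narrows the half-width for a dose difference from about 1.12 to 0.97 log10. The variance ratio is 0.75, or 0.65 to 0.85 for r from 0.3 to 0.7. These figures rest on assumed SDs and correlations, equal spread at baseline and follow-up, and complete data. With no imputation, and an efficacy population that generally requires all three doses and two weeks of follow-up, n may be below 15.

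A reader might infer more than the documents support:

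- That the plan omits any measure of spread. SAP section 3 and protocol 12.1 require the SD; the table shell does not show it.
- That the plan formally compares doses on this endpoint. It does not.
- That baseline imbalance is left in entirely. The change score removes part of it, and a share (1 − r) remains. Days since onset is not addressed.
- That any imbalance is only chance. Non-randomised groups and sequential opening of the arms mean it may be systematic.
- That adjustment would make the dose ranking reliable. Under the central assumptions the adjusted interval is still about ±1 log10, and its main value is to show that limit.

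**What to change.** 1. In Table 12.1.7, show n, SD and the 95% CI of the mean change at each visit. The SD brings the shell into line with SAP section 3; the CI is new.
2. For Days 4 and 7, add a supportive, exploratory ANCOVA of log10 viral load on dose, baseline log10 viral load and days from symptom onset to first dose. Report adjusted means, and dose differences or a linear dose trend, with 95% CIs.
3. State how undetectable results enter the log10 analysis, either as a fixed value or as censored observations.
4. State beside the results that the first patients in arm A and the last initial group in arm C were not randomised, that the arms opened in sequence, and that the model does not remove calendar-time effects.
5. While editing, reconcile the visits: Day 15 is in Table 12.1.7 but not in the mean-change list in SAP 8.1. Also reconcile the group size in SAP 3.1.4 (6 in the heading, 9 in the text).

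The cost is one exploratory model, a few table columns and a written rule for undetectable values. No new data are needed. The price in interpretation is one more exploratory result that must not be read as a test of dose.
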